12. TREATMENT OF SUBJECTS

12.1 Identity of Study Treatment(s)

12.1.1 OV101

A horizontal bar chart with 10 categories on the x-axis and 1000 samples on the y-axis. The bars are black and the chart has a light gray background with a vertical grid line at the 500 mark.

| Category | Approx. Sample Range |
|----------|----------------------|
| 1 | 100-150 |
| 2 | 100-150 |
| 3 | 100-150 |
| 4 | 100-150 |
| 5 | 100-150 |
| 6 | 100-150 |
| 7 | 100-150 |
| 8 | 100-150 |
| 9 | 100-150 |
| 10 | 100-150 |

12.1.2 Placebo

Placebo will be provided as a visually matching capsule, without active ingredient.

12.1.3 Administration of Study Treatments

OV101 will be supplied as a 5 mg capsule, and matching placebo, in bottles. The caregiver will receive a sufficient number of capsules in 1 bottle "Morning" and 1 bottle "Evening" at the baseline visit and at the Week 6 interim visit.

All subjects will receive a morning dose of OV101 or placebo and an evening dose of OV101 or placebo during the entire duration of treatment. Two dosing schedules of OV101 will be assessed; a single evening dose (Schedule A: QD) based on what was previously clinically assessed in the treatment of sleep disorder, and a morning plus evening dose (Schedule B: BID) designed to provide a more sustained exposure. Schedule C is morning and evening placebo (BID). All subjects will be up-titrated to the target dose unless this target dose is not tolerated (for titration conventions see below). All subjects will receive treatment for a maximum of 12 weeks at their highest tolerated dose. The last dose of study drug should be taken the morning of the Day 84 visit if the subject is on the BID dosing regimen.

Given the potential effects with food previously described:

- For the morning dose, it is recommended that the study drug be given with or shortly after the morning meal
- For the evening dose, it is recommended that study drug be given within 30 minutes of scheduled bedtime

The capsules can be opened and content added to one spoon of semi-liquid food (applesauce, pudding etc.). CAPSULE CONTENT CANNOT BE PLACED IN LIQUID. It must be documented specifically how the capsules were taken e.g. swallowed whole or taken in one spoon of applesauce or other food.

12.1.3.1 Titration Conventions

Doses will be progressively increased in 5 mg increments (OV101 or placebo) (Table 2) to a target of 15 mg (3 capsules) in the evening and 10 mg (2 capsules) in the morning for each subject which will deliver the target dose of 15 mg OV101 as an evening dose in Schedules A and B, and 10 mg OV101 as a morning dose in Schedule B. Each dose-escalation will be performed after adequate tolerability has been assessed by caregiver and investigator during a phone visit. Unscheduled study center visits are optional at any time to confirm tolerability.

The decision to up- or down-titrate will be at the investigator's discretion. The study center will document each titration step in the eCRF and in source documents. The AEs triggering any down-titration must be recorded. The study center will provide the caregiver with written dosing instructions until the next titration step, via fax, e-mail, or during an unscheduled on-study center visit.

Details for target up-titration, slowed titration, and down-titrations are provided in Sections 12.1.3.4, 12.1.3.5, and 12.1.3.6, respectively."

12.1.3.2 Titration Scheme

Table 2 summarizes the titration scheme.

Table 2 Study Titration Schedule

| Schedule/Time | | Days 1 to 2 | Days 3 to 6 | Days 7 to 9 | Days 10 to 13 | Day 14* |
|---------------|---|-------------|-------------|-------------|---------------|---------|
| S T | ■ | ■ | ■ | ■ | ■ | ■ |
| | ■ | ■ | ■ | ■ | ■ | ■ |
| T S | ■ | ■ | ■ | ■ | ■ | ■ |
| | ■ | ■ | ■ | ■ | ■ | ■ |
| S T | ■ | ■ | ■ | ■ | ■ | ■ |
| | ■ | ■ | ■ | ■ | ■ | ■ |

* To end-of-study treatment period

12.1.3.3 Titration Initiation

Day 1: Treatment can start on any day during the week. The next up-titration will occur on Day 3. If the defined interval occurs during the weekend, a +2 day window for next titration step is acceptable, but the investigator should consider scheduling the start of treatment appropriately to limit titration steps occurring during the weekend. All subjects will start with 1 capsule (OV101 or placebo) in the evening.

12.1.3.4 Target Up-Titration

Day 3 (window + 2 days): If no AE related to study treatment is observed from the previous time point by caregiver and/or the investigator, another OV101 or placebo capsule is added in the evening.

Day 7 (window + 2 days): If no AE related to the study treatment is observed from the previous time point by caregiver and/or the investigator, another OV101 or placebo capsule is added in the evening.

Day 10 (window + 2 days): If no AE related to the study treatment is observed from the previous time point by caregiver and/or the investigator, another OV101 or placebo capsule is added in the morning.

Day 14 (window + 2 days): If no AE related to the study treatment is observed from the previous time point by caregiver and/or the investigator, another OV101 or placebo capsule is added in the morning.

12.1.3.5 Slowed Up-Titration

If tolerability does NOT allow immediate further dose-escalation at any of the above detailed days (3, 7, 10, or 14), but does at subsequent visit (e.g. Day 10 instead of Day 7), delayed up-titration will also be acceptable. In this case, the investigator will record up-titration data during the additional phone titrations calls. Any such intolerance must be documented as an AE.

12.1.3.6 Down-Titration

Modifications may be made per investigator judgment on urgent need or medical necessity. If tolerability is not acceptable (e.g. somnolence, dizziness, vomiting, or change in behavior) after a previous up-titration step or during the course of the 12 weeks of treatment, the Investigator should discuss with the Sponsor MM or his/her delegate if necessary. Any such intolerance must be documented as an AE. Once a tolerable dose has been reached, it shall remain constant for the duration of the treatment period.

12.1.3.7 Ongoing Treatment

Day 14: Earliest day the target dose can be reached (10 mg [2 capsules] in the morning and 15 mg [3 capsules] in the evening): if so, dosing should be kept stable until End of Treatment visit (Week 12) unless intolerance requires down-titration according to the above described conventions.

12.2 Study Treatment Packaging and Labeling

12.2.1 Packaging

OV101 will be supplied as a 5 mg capsule, and matching placebo, in 75 mL bottles containing 90 capsules for morning and 120 mL bottles containing 140 capsules for evening. The caregiver will receive a “Morning” bottle and an “Evening” bottle at Baseline and Week 6, respectively. Depending on the allocated treatment group, the “Morning” or “Evening” bottles will contain the following:

- Group A (QD): Morning – Placebo/Evening – OV101

- Group B (BID): Morning – OV101/Evening – OV101
- Group C (Placebo): Morning – Placebo/Evening – Placebo

12.2.2 Labeling

Bottles containing OV101 or matching placebo, will have color tinted labels marked “Morning” (yellow label) or “Evening” (blue label). Labels will include the Sponsor Name (Ovid Therapeutics Inc.), protocol number, bottle number (based on randomization), expiration date, number of capsules (each bottle), “Morning” or “Evening” and “Take as directed”, as well as storage specifications. Each bottle will be labeled with an English and Spanish label. Bottles and study treatment will be distributed by unique bottle number as designated by the IWRS and bottle quantities will be supplied to each study center in accordance with IWRS.

12.2.3 Storage

Study treatment must be received by a designated person at the study center, handled and stored safely and properly, and kept in a secured location to which only the investigator and designated staff have access. Study treatments are to be dispensed only in accordance with the protocol. The investigator is responsible for keeping accurate records of study treatment supplies received from Ovid Therapeutics Inc., the amount dispensed to and returned by the subjects, and the amount remaining at the conclusion of the study. Study treatment should be stored at $\leq 86^{\circ}\text{F}$.

12.3 Blinding and Randomization to Study Treatments

This is a double-blind, placebo-controlled study. Investigators, study staff, and study subjects will be blinded to the randomized study treatment assignments. Both randomization and blinding techniques will be used in this study to minimize bias. A computer-generated randomization schema will be centrally available via IWRS to all clinical centers that meet the requirements for participation in the study. The IWRS system can be accessed by individuals who have been issued a user ID and password, such as individuals at the study center or individuals from [REDACTED]

[REDACTED]
[REDACTED]
[REDACTED] Caregivers and investigators will also be asked at the End of Treatment visit whether they believe the subject was in an OV101 or placebo treatment arm.

12.4 Procedure for Breaking the Randomization Code

In most cases, study drug unblinding will not be necessary. In a medical emergency where knowledge of the subject’s treatment assignment may influence the subject’s clinical care, the investigator, and if applicable, designated personnel at [REDACTED] may access the subject’s treatment assignment. The study center investigator and appropriate [REDACTED] project team members will be authorized to access the emergency unblinding functionality within the IWRS. The system will require the user to enter an authorization key number to complete the emergency unblinding transaction. The exact description of the treatment assigned to the individual subject then will be accessible. Emergency

unblinding can thus be made for any subject without affecting the double-blind nature of the study. Subject treatment information may only be accessed in the event of an emergency and out of necessity to know the identity of the allocated study drug to institute appropriate therapeutic management. The investigator should make every effort to discuss the rationale for emergency unblinding with the [REDACTED] Medical Monitor prior to unblinding the individual subject. Emergency unblinding should only be considered in situations where the knowledge of the treatment code has an impact on the planned treatment of the emergency. Once the randomization code is broken for a subject, he/she must be withdrawn from the study.

Should a situation arise where unblinding is urgently required (i.e. knowledge of treatment code is required to adequately manage a life-threatening situation), the investigator at that study center may perform immediate unblinding through IWRS without the need for communication with the [REDACTED] Medical Monitor.

In the event that emergency unblinding is performed, the investigator can view and must print the blinded confirmation document from IWRS. The investigator must record on the confirmation document printout the reason for the emergency unblinding, and sign the document. The confirmation document must then to be kept in a safe place until the end of the study. Once a randomization code has been broken, the investigator must inform the [REDACTED] Medical Monitor in writing within 24 hours. The investigator is strongly advised not to divulge the subject's treatment assignment to any individual not directly involved in managing the medical emergency, nor to personnel involved with the analysis and conduct of the study. The investigator can contact Ovid Therapeutics Inc. or their designee to discuss such situations without divulging subject's treatment assignment.

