11.4 Withdrawal of Subjects

A subject may voluntarily withdraw at any time and for any reason. If a subject withdraws, at his or her request or at the request of his or her caregiver or legal representative, the reason(s) must be recorded on the relevant page of the subject's eCRF. Subjects who withdraw from the study prematurely should undergo all end-of-study assessments where possible. It is vital to obtain follow-up data on any subject withdrawn because of an AE. In any case, every effort must be made to undertake protocol-specified safety follow-up procedures. If a subject refuses to continue with study procedures, the reason for refusal should be fully documented in the subject's source document and recorded in the study specific eCRF. Subjects who withdraw from the study prior to completing the final follow-up visit may be replaced at the discretion of Ovid Therapeutics Inc.

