13.1.1 Withdrawal from the Study

Subjects or their caregiver may withdraw subjects from the study at any time for any reason without compromising the subject's medical care. The investigator may also withdraw subjects from the study.

Subjects who withdraw from the study prior to the End of Treatment visit should complete the procedures scheduled for that visit. The reason for subject withdrawal will be recorded in the eCRF.

Withdrawal of subjects for any reason should be discussed with the Medical Monitor.

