13.1.2 Discontinuation of Study Drug

If it is necessary to discontinue the study drug earlier than planned, subjects should continue to be followed per protocol to capture safety and efficacy assessments for the duration of the study period if feasible.

The investigator may withdraw the subject from the study drug for the following reasons:

- Upon subject's or caregiver's request
- The subject or caregiver is unwilling or unable to adhere to the protocol-specified visits
- The subject experiences an intolerable AE
- During the study, the subject develops symptoms or conditions listed in the exclusion criteria
- Other medical reason, at the discretion of the investigator and/or the Medical Monitor

Subjects who discontinue the study due to an AE considered related to study drug should be followed until the event is resolved, considered stable, or the investigator determines the event is no longer clinically significant. Study drug discontinuation due to AEs considered not related to study drug will be followed until resolution.

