16.1 Adverse Events

16.1.1 Definitions

The definitions for TEAEs, AEs, and SAEs are given below. The Principal Investigator is responsible for ensuring that all study center staff are familiar with the content of this section. Any AE experienced by the subject between the screening visit (Day -28) and up to completion of the follow-up period after the last administration of study drug (Day 98 follow-up phone visit) must be recorded on the eCRF, regardless of the severity of the event or its relationship to study treatment.

Adverse Event (AE)

An AE is defined as any untoward medical occurrence in a clinical investigation subject, administered a pharmaceutical product, and which does not necessarily have a causal relationship with this treatment. An AE can therefore be any unfavorable and unintended sign (including an abnormal laboratory finding), symptom or disease temporally associated with the use of a medicinal (investigational) product, whether or not related to the medicinal (investigational) product.

Determination of whether an abnormal laboratory value meets the definition of an AE will be made by the investigator. Although abnormal laboratory values are typically not considered AEs, the following considerations may result in an abnormal laboratory value being considered an AE:

- A laboratory test result meets the criteria for an SAE
- A laboratory test result requires the subjects to receive specific corrective therapy
- A laboratory abnormality that the investigator considers to be clinically significant

Any intolerance that triggers a dose reduction during the titration period must be documented as an AE.

Treatment-Emergent Adverse Event (TEAE)

A treatment-emergent adverse event (TEAE) is defined as an AE with an onset that occurs after receiving study drug (AE start date \geq first dose date) and within 30 days after receiving the last dose of study drug (AE start date minus last dose date \leq 30), or an AE that occurs pre-treatment but worsens post treatment.

Serious Adverse Event (SAE)

An SAE is any untoward medical occurrence that at any dose:

- Results in death

- In the view of the investigator, places the subject at immediate risk of death (a life-threatening event); however, this does not include an event that, had it occurred in a more severe form, might have caused death

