16.1.1.2 Recording of Adverse Events

For the purposes of this study, any detrimental change in the subject's condition, from the screening visit (Day -28) and up to completion of the follow-up period after the last administration of study drug (Day 98 follow-up phone visit) should be considered an AE and must be recorded on the eCRF.

All SAEs and AEs will be recorded starting from the screening visit (Day -28).

All ongoing AEs should be followed up for 30 days after the last administration of study drug, with the exception of any ongoing study drug-related AEs, which should be followed until resolution, unless in the investigator's opinion, the AE is unlikely to resolve due to the subject's underlying disease. Any new SAEs occurring up to 28 days after the last administration of study drug (Day 98 follow-up phone visit) should be reported according to Section 16.1.1.6.

At any time after the follow-up visit, if an investigator learns of an SAE that can be reasonably related to study drug, he/she should promptly notify Ovid Therapeutics Inc.

The severity of AEs and SAEs will be graded using the National Cancer Institute Common Terminology Criteria for Adverse Events (CTCAE, Version 4). Any AE not listed in the CTCAE will be graded as follows:

| Severity Grade | Definition |
|----------------|------------------------------------|
| 1 | Mild AE |
| 2 | Moderate AE |
| 3 | Severe or medically significant AE |
| 4 | Life-threatening AE |
| 5 | Death related to AE |

It is important to distinguish between serious and severe AEs. Severity is a measure of intensity whereas seriousness is defined by the criteria in Section 16.1.1.

An AE of severe intensity need not necessarily be considered serious. For example, nausea that persists for several hours may be considered severe nausea, but not an SAE. On the other hand, a stroke that results in only a limited degree of disability may be considered a mild stroke but would be an SAE.

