17.2.3.2 Safety Variables

The following safety variables will be evaluated:

- SAEs, and TEAEs throughout the study, TEAEs leading to study discontinuation, treatment-related TEAEs, and TEAEs of special interest
- Clinical safety laboratory values at Weeks 6 and 12
- Suicidality (using the ABC-C Irritability subscale) at Weeks 6 and 12
- Vital signs at Weeks 6 and 12
- EEG and seizure diary assessments from baseline to end-of-study
- Physical Exam at weeks 6 and 12

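### Section 12.4 makes study withdrawal mandatory after emergency unblinding, although stopping study drug and continuing follow-up under Section 13.1.2 would be enough

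*Combined protocol and SAP*

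**What the plan says.** Protocol Section 12.4 limits code breaks to medical emergencies in which knowing the treatment affects care. It then states without exception: "Once the randomization code is broken for a subject, he/she must be withdrawn from the study".

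Section 13 separates two outcomes:

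- **Study drug stopped (13.1.2):** "subjects should continue to be followed per protocol to capture safety and efficacy assessments for the duration of the study period if feasible".
- **Withdrawn from the study (13.1.1):** "Subjects who withdraw from the study prior to the End of Treatment visit should complete the procedures scheduled for that visit".

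Other clauses protect withdrawn subjects:

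- Section 11.4 calls follow-up vital when the withdrawal is due to an AE, and adds: "In any case, every effort must be made to undertake protocol-specified safety follow-up procedures".
- The last paragraph of 13.1.2 keeps subjects who leave the study for a drug-related AE under follow-up until the event resolves, is stable or no longer matters clinically.
- Section 10.1.3.4 gives early withdrawals the Week 12 safety measures, including the irritability subscale of the Aberrant Behavior Checklist (ABC-I), and waives efficacy.
- Section 16.1.1 requires recording of "Any AE experienced by the subject between the screening visit (Day -28) and up to completion of the follow-up period", which it ties to the Day 98 call. Section 16.1.1.2 repeats the span: "from the screening visit (Day -28) and up to completion of the follow-up period after the last administration of study drug". Neither exempts withdrawn subjects.

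**The concern.** The primary objective is safety and tolerability from Baseline to Week 6 and Week 12. A subject whose code is broken has had a medical emergency, so the later course is more informative than that of a typical dropout. Section 12.4 nevertheless puts this subject in the category with less scheduled follow-up.

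The result is uneven on the protocol's own terms. Section 13.1.2 lists an intolerable AE as a reason to stop drug, and a subject who stops for that reason remains in scheduled follow-up. A subject with the same event whose code is looked up must leave the study. The extent of follow-up then depends on a query to the randomization system and not on clinical need.

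At stake are new events that a scheduled call or visit would have prompted the caregiver to report, and safety values at the times named in Section 17.2.3.2, for example "Clinical safety laboratory values at Weeks 6 and 12". A duty to record AEs is not the same as a contact that elicits them.

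**Working it through.** **The plan's own figure.** Section 17.1 gives the half-width of the 95% confidence interval (CI) for a 25% AE incidence: 1.96 × √(0.25 × 0.75 / n).

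- n = 25: 16.97%, stated as 17%.
- n = 20: 18.98%, stated as 19%.

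Both reproduce, and 12.4 does not alter them. The Safety Analysis Set includes everyone with at least one dose, so an unblinded subject stays in the denominator. Follow-up is less complete, but n does not shrink.

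**Inputs.** From the protocol's Table 1, the scheduled contacts after titration are Days 31, 43, 57, 71, 84 and 98. Laboratory tests and vital signs fall on Days 43 and 84. The TEAE definition in Section 16.1.1 runs to "within 30 days after receiving the last dose of study drug". SAP Section 3.9.1 states no upper limit, so the protocol's window is the narrower one and is used here.

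**Assumptions.** Nominal visit days; last dose on the day of unblinding.

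**Contacts already covered.** Day 84 is not counted as a lost contact, because 13.1.1 and 10.1.3.4 move its safety procedures to the exit visit; only the timing changes. Day 98 is not counted, because AE recording runs to that call.

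| | Unblinded Day 14 | Unblinded Day 43, after the visit |
|---|---|---|
| Contacts still scheduled | 31, 43, 57, 71, 84, 98 (six) | 57, 71, 84, 98 (four) |
| Less Days 84 and 98 | 6 − 2 = 4: Days 31, 43, 57, 71 | 4 − 2 = 2: Days 57, 71 |
| TEAE window closes | 14 + 30 = Day 44 | 43 + 30 = Day 73 |
| Of these, inside the window | Days 31, 43 (two) | Days 57, 71 (two) |
| Planned laboratory and vital-sign times not kept | Days 43, 84 (two) | Day 84 (one) |

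In the first column Day 43 appears both as a contact and as a laboratory time, so those rows should not be added. The exit visit returns one set of safety assessments at an unplanned day.

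**Share of an arm.** One such subject is 1/25 = 4% of a 25-subject arm, or 1/20 = 5% of a 20-subject arm, at a planned time point.

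**The case against.** The strongest reply is that 12.4 is a permissible choice with a sensible motive. The Clinical Global Impression (CGI) scales are completed by caregiver and investigator, and ABC-I is caregiver-reported and reviewed by the investigator. Ratings after a code break may be biased. This stands, and it is why ABC-I and efficacy ratings are not counted as losses here. It is much weaker for laboratory values and vital signs, and flagging can deal with the ratings.

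The triggering emergency is followed under either category, and 11.4 may be read as reaching the intermediate contacts too. The first part stands. The second is possible, but 11.4 names no visits, so those contacts rest on interpretation.

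Late values may also say little about drug effect. Section 10.3 gives a half-life of about 1.5 hours, and Section 10.1.3.2 reports no withdrawal effects after chronic dosing. This lowers the value of a Day 84 sample taken weeks off drug, but does not remove the interest in contacts inside the TEAE window.

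Finally, 13.1.2 is itself only a request, where feasible. That is true, but it expressly asks for per-protocol follow-up to the end of the study period, which no withdrawal clause does.

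**Conclusion.** The point holds as a small improvement to the design. For a subject unblinded on Day 14, up to four prompted contacts and two on-schedule laboratory and vital-sign times are not expressly kept. After the Day 43 visit the figures are two and one. In each case two of the contacts lie inside the 30-day TEAE window. These counts rest on nominal visit days and a last dose on the day of unblinding. The documents give no unblinding rate and describe unblinding as seldom needed, so the number affected may be zero.

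A reader might infer more in three ways, none of which the documents support:

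- **That 12.4 contradicts 13.1.2.** It does not. The two sections govern different categories, and 12.4 simply picks the stricter one.
- **That all safety follow-up ends, or that all six (or four) remaining contacts are lost.** The exit visit, AE recording to the Day 98 call and follow-up of the triggering event remain.
- **That the primary TEAE incidence is materially distorted.** The triggering event would ordinarily already make the subject a TEAE case, and the subject stays in the denominator.

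The efficacy waiver in 10.1.3.4 applies to every early withdrawal and is not a consequence of 12.4.

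**What to change.** Replace the sentence in 12.4 with wording such as: *After an emergency code break, study drug is permanently stopped; the subject stays in the study and is followed under Section 13.1.2 through the Day 98 call where feasible, unless consent is withdrawn.*

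In the SAP, flag unblinded subjects in the listings. Either exclude their CGI, ABC-I and other rated outcomes after the code break from the main summaries, or show results with and without them.

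The cost is a protocol amendment, probably with ethics board approval, since Section 20.1 exempts only logistical or administrative changes. It also needs a short SAP addition and separate handling of a few unblinded ratings if a case occurs. No contacts are added beyond those already scheduled, and sample size and precision do not change.
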